6.6.2.1.4. Binary Analyses

A binary analysis of KCCQ-OS, similar to the analysis described for 6-MWT in Section 6.6.1.4, will be conducted using a threshold of a ≥ 0 point increase in KCCQ-OS from baseline to Month 12.

6.6.2.2. Composite All-cause Mortality, Frequency of CV Events (CV hospitalizations and urgent HF visits), and Change from Baseline in 6-MWT over the 12-month Double-blind Period

6.6.2.2.1. Definition of Estimand

For the objective of evaluating the efficacy of patisiran compared with placebo on patient mortality, hospitalizations and urgent HF visits, and change from baseline in 6-MWT, the estimand is defined as follows:

- **Target patient population:** Patients with hATTR or wtATTR amyloidosis with cardiomyopathy. Patients may or may not be taking tafamidis at study entry.
- **Treatment condition:** Patisiran 0.3 mg/kg or placebo administered as an IV infusion q3W with or without concomitant use of tafamidis.
- **Endpoint:** Hierarchical comparison of all-cause mortality, frequency of CV events, and the change from baseline in 6-MWT over the 12m-DB period.
- **Population-level summary:** Stratified win ratio for the composite outcome between the patisiran and placebo arms.

Intercurrent events and strategies: Intercurrent events include treatment discontinuation, serious COVID-19 AE, COVID-19 related deaths and CV events, tafamidis drop-in, missing dose(s) due to COVID-19, inability to walk due to progression of ATTR amyloidosis, and heart

transplantation and ventricular assist device placement. They require different handling strategies, which are described in [Table 4](#) below.

Table 4: Intercurrent Event Strategies for the Analysis of the Composite Endpoint

Intercurrent Event	Handling Strategy
Treatment discontinuation	Treatment policy strategy: Intercurrent event is ignored; deaths, CV events, and 6-MWT assessments that occur after treatment discontinuation will be included in analysis.
COVID-19 related death and CV events	Hypothetical strategy: Deaths and CV events due to COVID-19 will be excluded from analysis. The goal is to estimate the treatment effect in a hypothetical setting where the COVID-19 pandemic is not present.
Serious COVID-19 AE	Hypothetical strategy: 6-MWT assessments obtained on or after the onset of a serious COVID-19 AE will be treated as missing.
Tafamidis drop-in (ie, taking tafamidis for more than 28 days after randomization) in the subgroup of patients who were not on tafamidis at baseline	Treatment policy strategy: Intercurrent event is ignored; deaths, CV events, and 6-MWT assessments that occur after tafamidis drop-in will be included in analysis.
Missing dose(s) due to COVID-19	Treatment policy strategy: Intercurrent event is ignored; deaths, CV events, and 6-MWT assessments that occur after missing dose(s) due to COVID-19 will be included in analysis.
Heart transplantation and ventricular assist device placement	Composite variable strategy: Heart transplantation and ventricular assist device placement will be treated in the same manner as death.

6.6.2.2.2. Primary Analysis

The composite endpoint of all-cause mortality, frequency of CV events (CV hospitalizations and urgent HF visits) and change from baseline in 6-MWT will be analyzed using the stratified win ratio method, [Dong 2018] stratified by baseline tafamidis use (yes vs. no). This method makes within-stratum pairwise comparisons (for all possible patisiran/placebo patient pairs) of the 3 components in the hierarchical order specified above. Within a stratum, each patisiran patient will be compared with all placebo patients in a stepwise fashion, with the “winner” assigned a score of +1 and the “loser” assigned a score of “-1”. The detailed steps are described as follows. All comparisons will be based on data collected during the 12m-DB period.

Step 1: compare all-cause mortality

The comparison of the two patients will be performed at the shorter of their survival follow-up times.

- If both patients are deceased, then the patient with a longer survival time is assigned a +1 and the other is assigned a -1
- If one patient is alive and the other is deceased, the alive patient is assigned a +1 and the deceased patient is assigned a -1

- Otherwise, proceed to step 2

Step 2: compare frequency of CV events

The comparison of the two patients will be performed at the shorter of their follow-up times while patients remain on the study.

- The patient with fewer CV events is assigned a +1 and the other is assigned a -1
- If the numbers of CV events are the same, go to step 3

Step 3: compare change from baseline in 6-MWT

- The patient who has less decline in 6-MWT at Month 12 is assigned a +1 and the other is assigned a -1. A patient who is unable to walk will be assigned as -1 when compared with another patient who is able to walk.
- If one or both patients have missing data at Month 12, compare change from baseline in 6-MWT at the latest common study visit where both patients had a 6-MWT assessment. The patient who has less decline in 6-MWT is assigned a +1 and the other is assigned a -1. A patient who is unable to walk will be assigned as -1 when compared with another patient who is able to walk.
- If tied or undetermined, assign score 0 to each patient

The point estimate of the stratified win ratio (WR) is defined as

$$WR = \frac{\sum_{m=1}^2 n_t^{(m)} / N^{(m)}}{\sum_{m=1}^2 n_c^{(m)} / N^{(m)}}$$

where $n_t^{(m)}$ and $n_c^{(m)}$ are the number of patisiran/placebo pairs in stratum m in which the patisiran patient was the winner and in which the placebo patient was the winner, respectively, and $N^{(m)}$ is the total number of patients in stratum m .

A 95% CI and p value for the stratified win ratio will be estimated (see Section 9.2 for details).

6.6.2.3. Composite All-cause Mortality and Frequency of All-cause Hospitalizations and urgent HF visits over the 12-month Double-blind Period in Patients Not on Tafamidis at Baseline

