Inability to walk due to progression of ATTR amyloidosis (including patients who are unable to walk due to hospitalization related to progression of ATTR amyloidosis) ^a	Composite variable strategy: For patients who are unable to walk due to progression of ATTR amyloidosis, the missing Month 12 6-MWT change from baseline will be imputed as the worst 10 th percentile change observed across all patients in the 12m-DB period, capped by the worst possible change for the patient (ie, 0 – baseline 6-MWT).
Death (including heart transplant and ventricular assist device placement) not due to COVID-19 ^a	Composite variable strategy: For patients who die (not due to COVID-19), the missing Month 12 6-MWT change from baseline will be imputed as the worst 10 th percentile change observed across all patients in the 12m-DB period, capped by the worst possible change for the patient (ie, 0 – baseline 6-MWT).
Death due to COVID-19	Hypothetical strategy: Missing data due to COVID-19 death will be assumed as MAR.

^a The imputed outcome will be used in the stratified Wilcoxon Rank Sum test and stratified HL estimate but will not be used in the descriptive summaries.

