6.6.1.2. Primary Analysis using the Stratified Wilcoxon Rank Sum Test and Hodges-Lehmann Estimate

The primary analysis will be performed using the stratified Wilcoxon Rank Sum test for the FAS, stratified by baseline tafamidis use (yes vs. no). The analysis will be based on the following assumptions for missing data at Month 12:

1. Patients who die during the 12m-DB period (not due to COVID-19) or who have become unable to walk due to progression of ATTR amyloidosis by Month 12 and have missing data: Assuming that deaths observed in the study will likely be related to worsening of disease, the missing Month 12 6-MWT change from baseline will be imputed as the

worst 10th percentile change, capped by the worst possible change for the patient (ie, 0 – baseline 6-MWT).

2. Patients who have missing data due to other reasons will be imputed assuming data are MAR. Since the pattern of missing data within patients may be non-monotone, multiple imputation will be conducted separately by treatment arm and baseline tafamidis use group using the Markov Chain Monte Carlo (MCMC) method. For each treatment arm/baseline tafamidis use group, the imputation model will include type of amyloidosis (hATTR vs. wtATTR), NYHA class (I/II vs. III), age at randomization (<75 vs. ≥75), baseline NT-proBNP (≤3000 ng/L vs >3000 ng/L), baseline 6-MWT, and all calculated values of change from baseline in 6-MWT at pre-specified visits.

Missing values will be imputed 100 times to generate 100 complete datasets using the procedures described above. The stratified Wilcoxon Rank Sum test will be applied to each imputed dataset for the change from baseline in 6-MWT at Month 12. The Z scores estimated from the stratified Wilcoxon Rank Sum test fit to each imputed dataset will be combined by applying Rubin's rules,[Rubin 1996; Rubin 1987] using SAS PROC MIANALYZE to produce inferential results for the *p* value.

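### Step 3 of the win ratio scores inability to walk as a loss without stating a cause, while its estimand names only inability due to ATTR progression and Table 4 has no row for it

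*SAP*

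**What the plan says.** All references are to the current SAP, Amendment 2.1.

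- **Estimand, 6.6.2.2.1.** The list of intercurrent events includes "missing dose(s) due to COVID-19, inability to walk due to progression of ATTR amyloidosis". No other inability to walk is listed. Of the listed events it says "They require different handling strategies, which are described in" Table 4.
- **Table 4.** There are rows for treatment discontinuation, COVID-19 deaths and CV events, serious COVID-19 AE, tafamidis drop-in, missed doses due to COVID-19, and transplant or assist device. There is no row for inability to walk. The serious COVID-19 row uses a hypothetical strategy: "6-MWT assessments obtained on or after the onset of a serious COVID-19 AE will be treated as missing".
- **Step 3, 6.6.2.2.2.** The first bullet compares the Month 12 change and adds "A patient who is unable to walk will be assigned as -1 when compared with another patient who is able to walk". The second begins "If one or both patients have missing data at Month 12, compare change from baseline in 6-MWT at the latest common study visit" and ends with the same unable-to-walk sentence. Neither bullet names a cause or mentions COVID-19.
- **Primary 6-MWT analysis, 6.6.1.1 and 6.6.1.2.** The unfavourable imputed value, the worst 10th percentile change, is tied to a cause: "For patients who are unable to walk due to progression of ATTR amyloidosis, the missing Month 12 6-MWT change from baseline will be imputed". Apart from deaths not due to COVID-19, which get the same value, the rule is "Patients who have missing data due to other reasons will be imputed assuming data are MAR".

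**The concern.** The scoring rule of a confirmatory test should carry out its estimand. Here the estimand limits the event to disease progression, the table that should give its strategy omits it, and the only operative sentence drops the limit. A programmer following Step 3 as written would score a fracture at Month 12 as a loss against every patient who can walk.

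Two things are at stake. First, events unrelated to disease or drug could be scored as the worst functional outcome in test 3, while test 1 treats the same missing walk as missing at random. Second, the algorithm can be coded in more than one way, both for unrelated causes and for a walk not done after a serious COVID-19 AE. That choice should be settled before unblinding.

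**Working it through.** **Texts side by side**

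| Patient with no Month 12 walk | Primary 6-MWT analysis | Win ratio estimand and Table 4 | Step 3 as written |
|---|---|---|---|
| Unable because of ATTR progression | Worst 10th percentile change, capped | Listed as an event; no row in Table 4 | Loses to any walker |
| Unable because of an unrelated injury | MAR multiple imputation | Not listed | Loses to any walker if read literally; latest common visit if the value is simply missing |
| Unable after onset of a serious COVID-19 AE | MAR | Post-onset assessments missing | Loses to any walker if read literally; no precedence stated |

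The third row is unsettled because Table 4 speaks of assessments obtained after onset, and a walk that was not done is not an assessment obtained.

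**Plan's own figures.** The SAP gives no power, event rate or count of patients unable to walk for the win ratio, so there is no figure to reproduce on this point. Its only related figure, power above 90% for the primary 6-MWT comparison (29 m, SD 75 m, 150 per arm), reproduces at 91.8% and is not in question.

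**Size of the literal reading**

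Inputs:
- Section 7.3 says 75% of patients are tafamidis-naïve. With 300 patients that is 225 and 75, or about 112 and 38 per arm.
- From 6.6.2.2.2, wins and losses in each stratum are divided by the stratum total before summing.
- Assumptions: a share q of 50-70% of pairs is decided at Step 3; an affected patient would otherwise win half of those comparisons; there are no ties; the true win ratio is 1.00; the k excess patients are all in one arm of the no-tafamidis stratum.

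Stratum weights:
- No tafamidis: 112 × 112 / 224 = 56
- Tafamidis: 38 × 38 / 76 = 19
- Share of the no-tafamidis stratum: 56 / 75 = 0.747

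Shift in the overall win share: d = (k/112) × q × 0.5 × (56/75) = k × q / 300. The win ratio becomes (0.5 − d) / (0.5 + d).

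| k | q | d | Win ratio |
|---|---|---|---|
| 3 | 0.5 | 0.0050 | 0.980 |
| 3 | 0.6 | 0.0060 | 0.976 |
| 3 | 0.7 | 0.0070 | 0.972 |
| 5 | 0.5 | 0.0083 | 0.967 |
| 5 | 0.6 | 0.0100 | 0.961 |
| 5 | 0.7 | 0.0117 | 0.954 |

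If the excess is in the placebo arm, the inverse applies.

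**Upper bound by simulation.** Assumptions: strata of 210 and 90, normal changes with SD 75 m, differences of 33 m and 20 m, every pair reaching Step 3, and earlier-visit comparisons behaving like Month 12. With the affected patients treated as missing, the win ratio is about 1.55. When they always lose:

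| Affected, patisiran / placebo | Win ratio |
|---|---|
| 3 / 3 | about 1.55 |
| 10 / 10 | about 1.47 |
| 6 / 0 | about 1.40 |
| 0 / 6 | about 1.65 |

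With no true effect, equal counts leave the ratio near 1.0, and 6 against 0 gives about 0.93 or 1.10 depending on the arm. The simulated SD of the log win ratio under no effect is about 0.135. The largest shift in the table above, ln(0.954) = −0.047, is therefore about 0.35 of that SD.

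**The case against.** The strongest reply is that Step 3 is shorthand. It implements an estimand that names one inability event, and the rest of the current efficacy text attaches the ATTR qualifier to that event. The Amendment 2.1 change log in 7.4 keeps the qualifier for the primary endpoint and records no widening. This is a natural reading, and it means the SAP cannot be said to have chosen an any-cause rule. It does not remove the defect: nothing in Step 3 or Table 4 says the sentence is shorthand, and the row that would say so is absent.

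A reader might infer three stronger points that the documents do not support:

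- **That the latest-common-visit fallback can never be reached for such a patient.** A patient with a fracture and no Month 12 walk also meets the second bullet's own condition. The unable-to-walk sentence is repeated there and may refer to status at the visit being compared. The order is unclear, not settled against the patient.
- **That Step 3 overrides the COVID-19 strategy.** Nothing says so. Table 4 gives serious COVID-19 AEs, not COVID-19 in general, their own rule for this endpoint. What is missing is precedence when no walk was performed.
- **That the rule biases the comparison or inflates type I error.** It applies to both arms alike, so a chance imbalance in unrelated events is random variation.

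It is also fair to say that tests 1 and 3 need not handle missing walks identically, since one imputes and the other compares pairs. The difference matters here because test 3 departs from its own estimand.

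**Conclusion.** The point stands as a conflict between the wording of a confirmatory scoring rule and its estimand. Step 3 is wider than the listed intercurrent event, Table 4 lacks the row the estimand refers to, and precedence over the serious COVID-19 rule is not fixed.

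The consequence is modest. Balanced cases pull a real effect towards 1; unbalanced cases add noise. An overall win ratio of 1.00 moves to about 0.97-0.98 for an excess of 3 such no-tafamidis patients in one arm and to about 0.95-0.97 for an excess of 5. This rests on the literal reading, the 112 and 38 per-arm split, 50-70% of pairs decided at Step 3, and counts of 3 and 5 chosen for illustration with no basis in the SAP. It merits correction because the third test in the hierarchy should have only one possible coding.

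**What to change.** - In both Step 3 bullets, restrict the rule to inability to walk caused by progression of ATTR amyloidosis, counting hospitalization related to progression, as Table 1 already does for the primary endpoint.
- State that inability from any other cause, or on or after the onset of a serious COVID-19 AE, is missing, so that the latest-common-visit comparison applies.
- Add a new Table 4 row describing this Step 3 rule. Do not reinstate the superseded Amendment 2 row, which imputed 0 minus baseline and does not match the current pairwise scoring.

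The cost is a few words in two bullets, one clarifying sentence and one table row. The primary 6-MWT analysis already needs the cause of inability, so no new data are required. The change should be made before unblinding.

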6.6.2.3.1. Definition of Estimand

For the objective of evaluating the efficacy of patisiran compared with placebo on the composite outcome of mortality, hospitalizations and urgent HF visits in patients not on tafamidis at baseline, the estimand is defined as follows:

- **Target patient population:** Patients with hATTR or wtATTR amyloidosis with cardiomyopathy who are not taking tafamidis at study entry.
- **Treatment condition:** Patisiran 0.3 mg/kg or placebo administered as an IV infusion q3W with or without concomitant use of tafamidis.
- **Endpoint:** Timing and frequency of all-cause deaths, all-cause hospitalizations and urgent HF visits over the 12m-DB period.

- **Population-level summary:** Hazard ratio (HR) for the composite outcome between the patisiran and placebo arms.

Intercurrent events and strategies: Intercurrent events include treatment discontinuation, COVID-19 infection, tafamidis drop-in, missing dose(s) due to COVID-19, and heart transplantation and ventricular assist device placement. They require different handling strategies, which are described in [Table 5](#) below.

Table 5: Intercurrent Event Strategies for the Analysis of the Composite Endpoint

Intercurrent Event	Handling Strategy
Treatment discontinuation	Treatment policy strategy: Intercurrent event is ignored; deaths, all-cause hospitalizations and urgent HF visits that occur after treatment discontinuation will be included in analysis.
COVID-19 related deaths, hospitalizations, and urgent HF visits	Hypothetical strategy: Deaths, all-cause hospitalizations and urgent HF visits due to COVID-19 will be excluded from analysis. The goal is to estimate the HR in a hypothetical setting where the COVID-19 pandemic is not present.
Tafamidis drop-in (ie, taking tafamidis for more than 28 days after randomization) in the subgroup of patients who were not on tafamidis at baseline	Treatment policy strategy: Intercurrent event is ignored; deaths, all-cause hospitalizations and urgent HF visits that occur after tafamidis drop-in will be included in analysis.
Missing dose(s) due to COVID-19	Treatment policy strategy: Intercurrent event is ignored; deaths, all-cause hospitalizations and urgent HF visits that occur after missing dose(s) due to COVID-19 will be included in analysis.
Heart transplantation and ventricular assist device placement	Composite variable strategy: Heart transplantation and ventricular assist device placement will be treated in the same manner as death.

6.6.2.3.2. Primary Analysis

The composite endpoint of all-cause mortality and frequency of all-cause hospitalizations and urgent HF visits in patients who are not on tafamidis at baseline will be analyzed using an Andersen-Gill model, including treatment, type of amyloidosis (hATTR vs. wtATTR), baseline NYHA class (I/II vs. III), and age at randomization (<75 vs. ≥75 years) as covariates.

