5.7. Multiple Comparisons/Multiplicity

Formal statistical hypothesis testing will be performed on the primary and secondary efficacy endpoints with all tests conducted at the nominal 2-sided 0.05 significance level. The overall familywise error rate will be controlled at the 2-sided 0.05 significance level for the primary and secondary endpoints by a hierarchical ordering procedure. Endpoints will be tested in the following pre-specified hierarchy:

1. 6-minute walk test (6-MWT) change from baseline at Month 12
2. Kansas City Cardiomyopathy Questionnaire Overall Summary (KCCQ-OS) score change from baseline at Month 12
3. Composite endpoint of all-cause mortality, frequency of CV events (CV hospitalizations and urgent HF visits), and change from baseline in 6-MWT over the 12-month double-blind period
4. Composite endpoint of all-cause mortality and frequency of all-cause hospitalizations and urgent HF visits over the 12-month double-blind period in patients not on tafamidis at baseline

5. Composite endpoint of all-cause mortality and frequency of all-cause hospitalizations and urgent HF visits over the 12-month double-blind period in the overall population

There will be no multiplicity adjustment for exploratory endpoints.

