6.6.2.3.3. Component Analysis

The components of the composite endpoint in patients not on tafamidis at baseline will be analyzed as follows. For all-cause mortality, Kaplan-Meier survival curves for each treatment group will be presented. The HR and corresponding 95% CI will be estimated from a Cox proportional hazards model including treatment as a covariate. Frequency of all-cause hospitalizations and urgent HF visits will be analyzed using Poisson regression with treatment, type of amyloidosis (hATTR vs. wtATTR), baseline NYHA class (I/II vs. III), and age at

randomization (<75 vs. ≥75 years) as covariates, adjusting for duration of follow-up (ie, include duration of follow-up as an offset).

6.6.2.4. Composite All-cause Mortality and Frequency of All-cause Hospitalizations and urgent HF visits over the 12-month Double-blind Period in the Overall Population

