6.6.2.4.2. Primary Analysis

The composite endpoint of all-cause mortality and frequency of all-cause hospitalizations and urgent HF visits will be analyzed using a modified Andersen-Gill model stratified by baseline tafamidis use (yes vs. no), including treatment, type of amyloidosis (hATTR vs. wtATTR), baseline NYHA class (I/II vs. III), and age at randomization (<75 vs. ≥75 years) as covariates.

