6.6.2.4.3. Component Analysis

The all-cause mortality component of the composite endpoint will be evaluated using analyses similar to those described in Section 6.6.2.3.3. Frequency of all-cause hospitalizations and urgent HF visits will be analyzed using Poisson regression with treatment, baseline tafamidis use (yes vs. no), type of amyloidosis (hATTR vs. wtATTR), baseline NYHA class (I/II vs. III), age at randomization (<75 vs. ≥75 years), and the treatment-by-baseline tafamidis use interaction as covariates, adjusting for duration of follow-up (ie, include duration of follow-up as an offset).

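### No variance estimator for repeat events within a patient is named for confirmatory tests 4 and 5, and *modified* Andersen-Gill is undefined; with model-based errors and unequal patient risk, their level would exceed 5%

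*SAP*

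**What the plan says.** References are to the current SAP, Amendment 2.1.

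- **Hierarchy (Section 5.7).** Five endpoints are tested in fixed order, "with all tests conducted at the nominal 2-sided 0.05 significance level", and "The overall familywise error rate will be controlled at the 2-sided 0.05 significance level". The fourth test concerns all-cause mortality, all-cause hospitalizations and "urgent HF visits over the 12-month double-blind period in patients not on tafamidis at baseline". The fifth is the same endpoint in all patients.
- **Test 4 (Section 6.6.2.3.2).** The composite "will be analyzed using an Andersen-Gill model, including treatment, type of amyloidosis", baseline NYHA class and age.
- **Test 5 (Section 6.6.2.4.2).** The composite "will be analyzed using a modified Andersen-Gill model stratified by baseline tafamidis use (yes vs. no), including treatment" and the same other covariates. Section 6.6.3 carries the *modified* model over to the exploratory cardiovascular composite.
- **Event counts (Sections 6.6.2.3.3, 6.6.2.4.3 and 6.6.3).** The frequency of events "will be analyzed using Poisson regression with treatment" and covariates, adjusted for follow-up time.

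No section defines *modified*. The change tables in Sections 7.1 and 7.2 discuss only how baseline tafamidis enters the model. No robust or sandwich variance, patient clustering, frailty term, dispersion parameter or negative binomial model appears for any of these analyses. The SAP also does not say that model-based errors will be used.

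**The concern.** One patient can contribute several hospitalizations or urgent visits plus a death. If some patients are more event-prone than their covariates show, their events cluster. An Andersen-Gill fit with model-based errors then counts correlated events as independent information, and Poisson regression as written sets the variance equal to the mean. Both standard errors come out too small.

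The gap stands out because the SAP settles this matter for its other confirmatory tests. It gives Rubin's rules for the walk test (6.6.1.2), a covariance structure with fallbacks and Satterthwaite degrees of freedom for KCCQ-OS (6.6.1.3, applied by 6.6.2.1.2), and a variance under the null for the win ratio (9.2). Only tests 4 and 5 have nothing. Two analysts following the text could report different p values for the same confirmatory test.

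**Working it through.** **1. The plan's own figure.** The main SAP's only power figure is for the walk test (Section 5.1). The weighted effect is 0.7 × 33 + 0.3 × 20 = 29.1 m, rounded to 29. With SD 75 and 150 per arm, SE = 75 × √(2/150) = 8.66, 29/8.66 = 3.35, and power = Φ(3.35 − 1.96) = 0.918. The stated figure above 90% reproduces, but it does not bear on tests 4 and 5. For those the SAP gives neither an event rate nor a power figure; Section 7.3 says only that the overall-population composite is not sufficiently powered.

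**2. Inputs.** From the SAP: 300 patients, 1:1, two-sided 0.05, and 75% not on tafamidis (Section 7.3), so 0.75 × 300 = 225 for test 4 (210 with the 70% of Section 5.1). Assumed, because the SAP is silent: μ = 0.25, 0.5 or 1.0 non-fatal events per patient-year; gamma frailty variance φ = 0 to 2; death 6% and dropout 5% per year. Treatment is the only covariate, so φ stands for heterogeneity left after adjustment.

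**3. Closed form.** With equal follow-up, the true variance is (1 + φμ) times the model-based variance, so the actual level is 2 × [1 − Φ(1.96/√(1 + φμ))]. For μ = 0.5 and φ = 1: 1 + φμ = 1.5, 1.96/1.225 = 1.60, level 11.0%.

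**4. Null simulation.** 4,000 trials per setting, 225 patients, 12 months. Entries are the actual level of Andersen-Gill with model-based errors, with the closed form in brackets:

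| μ | φ = 0 | φ = 0.5 | φ = 1 | φ = 2 |
|---|---|---|---|---|
| 0.25 | 4.2% (5.0) | 5.6% (6.5) | 7.3% (8.0) | 10.0% (11.0) |
| 0.5 | 5.0% (5.0) | 7.8% (8.0) | 10.0% (11.0) | 14.6% (16.6) |
| 1.0 | 4.7% (5.0) | 10.3% (11.0) | 14.6% (16.6) | 23.6% (25.8) |

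Simulated values sit a little below the formula because death and dropout shorten follow-up. At μ = 0.5 and φ = 1 the level is 10.6% with 210 patients and 11.3% with 300.

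**5. After the fix.** With a sandwich variance clustered on patient, the level is 4.6% to 5.9% over the whole grid. At μ = 0.5 and φ = 1 the robust SE is 1.196 times the model-based one, so model-based intervals are 1 − 1/1.196 = 16% too narrow.

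**6. Poisson.** Model-based Poisson behaves almost identically: 5.6% to 23.7% for φ of 0.5 to 2, and 4.4% to 5.8% with robust errors over the whole grid. By the closed form its SE is 1/√(1 + φμ) of the true one: 0.943 at φμ = 0.125, 0.816 at 0.5 and 0.577 at 2. Intervals are therefore about 6%, 18% and 42% too narrow.

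**7. Familywise error.** If all five nulls are true, an error needs test 1 to reject, so the variance used in test 4 is irrelevant. If nulls 1 to 3 are false and null 4 is true, familywise error is the probability that tests 1 to 4 all reject. This cannot exceed the local level of test 4. If tests were independent, it would equal that level times the probability r of reaching test 4. A local level of 10.0% would then give more than 5% once r exceeds 5/10.0 = 0.50.

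**The case against.** The strongest reply is that unspecified is not the same as wrongly specified. Andersen-Gill names an intensity model and its risk sets, and it can be fitted with a patient-clustered variance; *modified* may mean exactly that. The model came from the protocol, which is not shown and may define the term. A reader might infer from Section 6.6.2.3.2 that test 4 will use model-based errors. The text does not say so, and that reading should not be reported as fact.

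A reader might also infer that type I error will exceed 5%. The documents do not support that either. It needs both model-based errors and residual heterogeneity, and the SAP gives no event rate or between-patient variance. The top of the range combines the highest assumed rate with the highest assumed frailty, and adjustment for amyloidosis type, NYHA class and age will absorb some heterogeneity.

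Third, the Poisson models might be read as threatening the familywise claim. They cannot: they appear only in component and exploratory analyses.

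These points make the finding conditional but do not remove it. If *modified* means a robust variance, test 4 lacks the word and is the unprotected test. If it means something else, neither test has a stated protection. Gatekeeping limits when the problem bites, but fixed-sequence control assumes each test holds its own level. Section 7.3 says test 4 was added to gain power and precision, so its standard error matters.

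**Conclusion.** The concern stands in conditional form. The SAP leaves open the variance estimator for two confirmatory recurrent-event tests and describes their models differently without explanation. If model-based errors are used and patients differ in risk beyond the covariates, the local level of tests 4 and 5 is about 6% to 24% for 0.25 to 1.0 events per patient-year and frailty variance 0.5 to 2. It stays near 5% at frailty variance 0. The rates and variances are assumptions, and familywise error is affected only when the earlier tests are rejected.

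The Andersen-Gill part should be settled before unblinding because confirmatory p values depend on it. The Poisson part is of lower severity: it affects only the width of component and exploratory intervals, though there the method as written does set the variance equal to the mean.

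**What to change.** - **Sections 6.6.2.3.2, 6.6.2.4.2 and 6.6.3:** specify Andersen-Gill with a sandwich variance clustered on patient. Define *modified* or delete it, so that tests 4 and 5 use the same model wording apart from stratification by baseline tafamidis.
- **Sections 6.6.2.3.3, 6.6.2.4.3 and 6.6.3 (event counts):** replace Poisson with negative binomial regression with log follow-up time as offset, or keep Poisson with a robust variance.

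This takes about one sentence per section and a standard software option. If a robust variance was already intended for the Andersen-Gill models, nothing changes there except the text. Otherwise intervals become somewhat wider: by a factor of about 1.2 at 0.5 events per patient-year and frailty variance 1, and hardly at all without heterogeneity.
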